5.2.3 Early Withdrawal Visit

If the subject withdraws early from the study, the procedures described for Injection Cycle 2, Week 12 (see Section 5.2.2.2) should be completed, if possible.

PROTOCOL FINAL (INCLUDING AMENDMENT #2): 24 JANUARY 2018

6 TREATMENT OF SUBJECTS

6.1 Study Drugs Administered

This is a single-arm study and all subjects will receive the same study treatment.

At the Baseline Visit (Cycle 1), all subjects will be allocated a subject number after giving written informed consent. Following baseline assessments and confirmation of eligibility for the study, AbobotulinumtoxinA (1500 U) will be administered by i.m. injection as a split dose, in both the UL and LL (see Section 6.1.1).

In Cycle 2, all subjects will receive a second administration of AbobotulinumtoxinA (1500 U) given as a split dose, in both the UL and LL. The dose split (per limb and per muscle) may be different to the dose split given for the first administration of AbobotulinumtoxinA, but it must follow the same limits (see Section 6.1.1).

Each subject will also receive a personalised GSC and will be asked to perform GSC therapy daily throughout the study (from Baseline Visit to Final Visit). Details are provided in Section 6.1.2.

Note: For subjects receiving antivitamin K therapy the Investigator will have to ensure that the International Normalised Ratio (INR) is below 3.5 within 1 week prior to study treatment administration.

Subjects currently receiving oral anti-spasticity medications (e.g. Baclofen) may be included provided the dose will be kept constant during the study.

6.1.1 AbobotulinumtoxinA (Dysport)

The IMP, AbobotulinumtoxinA (Dysport[®]), will be supplied as a white lyophilised powder in a vial containing 500 U of BTX-A-haemagglutinin complex. A total dose of 1500 U will be used in each of two injection (treatment) cycles.

Each Dysport vial containing 500 U will be reconstituted with 2.5 mL sodium chloride for i.m. injection (0.9%). For the total dose of 1500 U, three vials will be used for each subject on each dosing occasion The total volume to be injected on each dosing occasion will be 7.5 mL.

In each subject, the dose of AbobotulinumtoxinA 1500 U will be split between the UL and LL. The dose given in each limb will be decided by the investigator, according to his/her clinical judgement, based on which limb was considered the primary TT limb at the Baseline Visit and prespecified limits (see dosing rules below).

The second administration of AbobotulinumtoxinA 1500 U will be given at the Week 12, Week 16 or Week 20 visit (after the first AbobotulinumtoxinA injection) (see Section 3.1). The primary TT will remain the same for both AbobotulinumtoxinA injections and the study duration.

The following dosing rules will apply:

- electrical stimulation will be used to target the injection sites;
- at least half the total dose (i.e. ≥750 U) must be injected in the primary TT limb. The rest of the dose is injected in the secondary TT limb;
- a maximum of 1000 U can be injected in an UL (even if it is the primary TT limb);
- there is no maximum dose that can be injected in a LL, provided that some remainder dose (out of the 1500 U total) is used for the UL injections;

PAGE 50/105

PROTOCOL FINAL (INCLUDING AMENDMENT #2): 24 JANUARY 2018

• the second injection (Week 12, 16 or 20) may be given in a different split to the first injection, at the discretion of the investigator. However, the same minimal/maximal rules apply, as described above.

Details of study drug packaging and supply are provided in Section 3.4.

Dose administration details will be recorded in the eCRF, including the doses administered and details of the muscle groups that were injected. List of recommended muscles to be injected based on subject needs is presented in Section 6.1.1.1 for upper limb and Section 6.1.1.2 for lower limbs. Any muscle injected will be recorded in the eCRF.

6.1.1.1 List of muscles recommended to be injected and Dysport Dosing by Muscle for Upper Limb Spasticity

MUSCLES	DOSES
Flexor carpi radialis (FCR)	100 – 200 U
Flexor carpi ulnaris (FCU)	100 – 200 U
Flexor digitorum profundus (FDP)	100 – 200 U
Flexor digitorum superficialis (FDS)	100 – 200 U
Flexor Pollicis Longus	100 – 200 U
Adductor Pollicis	25 – 50 U
Brachialis	200 – 400 U
Brachioradialis	100 – 200 U
Biceps Brachii (BB)	200 – 400 U
Pronator Teres	100 – 200 U
Triceps Brachii (long head)	150 – 300 U
Pectoralis Major	150 – 300 U
Subscapularis	150 – 300 U
Latissimus Dorsi	150 – 300 U

6.1.1.2 List of muscles recommended to be injected and Dysport Dosing by Muscle for Lower Limb Spasticity

MUSCLES	DOSES
Soleus muscle	300 – 550 U
Gastrocnemius Medial Head	100 – 450 U
Gastrocnemius Lateral Head	100 – 450 U
Tibialis posterior	100 – 250 U
Flexor digitorum longus	50 – 200 U
Flexor digitorum brevis	50 – 200 U
Flexor hallucis longus	50 – 200 U
Flexor hallucis brevis	50 – 100 U
Rectus femoris	100 – 400 U
Hamstrings	100 – 400 U
Adductor magnus	100 – 300 U
Adductor Longus	50 – 150 U
Adductor Brevis	50 – 150 U
Gracilis	100 – 200 U
Gluteus maximus	100 – 400 U

PROTOCOL FINAL (INCLUDING AMENDMENT #2): 24 JANUARY 2018

6.1.2 Second Study Therapy: GSC

At the first visit, the investigator will prescribe the rehabilitation programme for the GSC [12]. The GSC is a motivational tool, which will be described in detail in the Study Operational Manual. The physiotherapist will teach each subject the stretching postures and exercises to perform on a daily basis throughout the study. These will be tailored to the individual subject's needs and will form the GSC therapy. The main focus will be on the primary TT limb (as determined at the Baseline Visit) and then the other limb. All muscle groups requiring active training and/or stretching should be trained.

The subjects will be given a diary at the Baseline Visit. As part of the GSC, they will be asked to record in this diary each day whether they have performed the GSC therapy. A copy of the diary and details regarding diary completion will be provided in the Study Operational Manual.

Telephone calls will be made to the subjects every 2 weeks to encourage them, check the GSC therapy is being performed daily and that they are completing the diary. The exercises may be adjusted at study visits, based on the clinical judgement of the investigator or physiotherapist.

At each postbaseline FU visit, the subjects will return the diary. The investigator will count the number of days when GSC therapy was not performed and will record this in the eCRF.

6.2 Concomitant Medication/Therapy

All previous GSC or physiotherapy will be recorded in the eCRF.

It will be recorded if subject is naïve or non-naïve to BoNT treatment. If non-naïve to BoNT treatment, the dates of the first injection and last injection, details of which limbs were injected, and the BoNT brand and dose used in the last injection will be recorded in the eCRF.

Prior and concomitant medications for UL or LL spasticity, taken from 4 weeks prior to baseline through the study (including the subject's last study visit) will be recorded in the eCRF. Other prior and concomitant medications and nondrug therapies taken from 4 weeks prior to baseline through the study (including the subject's last study visit) will also be recorded in the eCRF.

For each therapy, the generic name or trade name, dosage, route, start and end dates and indication will be recorded in the eCRF.

The following concomitant medications are not permitted during this study (see also Section 4.2):

- any other form of BoNT is not allowed;
- drugs which affect neuromuscular transmission, such as aminoglycoside antibiotics, should be used with caution;
- any anti-spasticity medication (such as Baclofen, tizanidine, eperisone or benzodiazepines), which is expected to change in dosage during the study is not allowed (anti-spasticity medications on a stable dose are permitted).

The following concomitant medications are permitted during this study but they must be monitored closely and every effort should be made to keep their dose and dose regimen constant throughout the course of the study:

- changes in pain medication are acceptable if absolutely necessary and according to clinical judgment and will be recorded in the eCRF;
- concomitant use of anticholinergic drugs (which may potentiate systemic anticholinergic effects) is permitted if the dosage has been stable for 6 weeks prior to study treatment and is expected to remain at this stable dose throughout the study;

PROTOCOL FINAL (INCLUDING AMENDMENT #2): 24 JANUARY 2018

• anticoagulant treatment if INR > 3.5 during the study.

6.3 **Procedures for Monitoring Subject Compliance**

Administrations of AbobotulinumtoxinA will be administered at the clinic by the investigator.

Telephone calls will be made every 2 weeks to the subject to remind him/her to perform the GSC therapy every day and fill out the diary. At each postbaseline FU visit, subjects will return their diary. The diary will be checked and the number of days when GSC therapy was not performed since the last visit will be recorded in the eCRF.

The investigator will be responsible for monitoring subject compliance. Subjects can be withdrawn from the study at any time if the investigator or the sponsor determines that the subject is not in compliance with the study protocol (see Section 3.6).

PROTOCOL FINAL (INCLUDING AMENDMENT #2): 24 JANUARY 2018

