- Very rare cases of death, occasionally in a context of dysphagia, pneumopathy and/or in patients with significant asthenia have been reported after treatment with BTX-A or B. Patients with disorders resulting in defective neuromuscular transmission, difficulty in swallowing or breathing are more at risk of experiencing these effects. In these patients, treatment must be administered under the control of a specialist and only if the benefit of treatment outweighs the risk.
- Dysport should be administered with caution to patients with pre-existing swallowing or breathing problems including inhalation pneumopathy as these problems can worsen following distribution of its effect into the relevant muscles. Aspiration has occurred in rare cases and is a risk when treating patients who have a chronic respiratory disorder.
- Dysport should only be used with caution and under close supervision in patients with subclinical or clinical evidence of marked defective neuromuscular transmission (for example, myasthenia gravis). Such patients may have an increased sensitivity to agents such as Dysport, which may result in excessive muscle weakness.
- The recommended posology and frequency of administration for Dysport must not be exceeded.
- As with any i.m. injection, Dysport should be used only where strictly necessary in patients with prolonged bleeding times, or infection/inflammation at the proposed sites(s) of injection.
- Dysport contains a small amount of human albumin. The risk of transmission of viral infection cannot be excluded with absolute certainty following the use of human blood or blood products.
- Following Dysport treatment, a low number of patients developed neutralising antibodies.
- The effects of BTX may be enhanced by drugs interfering directly or indirectly with the neuromuscular function (for example, aminoglycosides, curare-like nondepolarising blockers) and such drugs should be used with caution in patients treated with BTX.
- The risk of excessive muscle weakness may impair the ability to drive or operate machinery.
- Patients and their caregivers must be warned of the necessity to seek immediate medical treatment in case of problems with swallowing, speech or respiratory problems.

PROTOCOL FINAL (INCLUDING AMENDMENT #2): 24 JANUARY 2018

PAGE 23/105

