4.2 Exclusion Criteria

Subjects will not be included in the study if any of the following exclusion criteria are met:

- (1) Inability to understand protocol procedures and requirements, which, in the opinion of the investigator, could negatively impact on protocol compliance, in particularly inability to exercise according to the GSC.
- (2) Previous surgery on the affected muscles and ligaments, tendons, nerve trunks, or bones of the treated upper or lower limb.
- (3) Previous treatment with phenol and/or alcohol in any of the treated limbs any time before the study.
- (4) Any medical condition (including severe dysphagia or breathing difficulties) that may increase, in the opinion of the investigator, the likelihood of AEs related to BoNT-A treatment.

PROTOCOL FINAL (INCLUDING AMENDMENT #2): 24 JANUARY 2018 PAGE 36/105

- (5) Subjects treated, or likely to be treated, with intrathecal baclofen during the course of the study or during the 4 weeks before study entry.
- (6) Current, planned or received within the last 4 weeks prior to study treatment, treatment with any drug that interferes either directly or indirectly with neuromuscular function (for example, aminoglycosides).
- (7) Major neurological impairment other than spastic paresis (including major proprioceptive ataxia or apraxia on the paretic side) that could negatively impact on the functional performance of the subject.
- (8) Known disease of the neuromuscular junction (such as Lambert-Eaton myasthenic syndrome or myasthenia gravis).
- (9) Known sensitivity to BoNT-A or any excipient of Dysport.
- (10) Infection at the injection site(s).
- (11) Current pregnancy or lactation. A pregnancy test will be performed at the start of the study for all female subjects of childbearing potential (i.e. not surgically sterile or 2 years postmenopausal).
- (12) Mental condition rendering the subject unable to understand the nature, scope and possible consequences of the study and/or evidence of an uncooperative attitude.
- (13) Abnormal baseline findings or any other medical condition(s) that, in the opinion of the investigator, might jeopardise the subject's safety.
- (14) Subjects who have participated in any therapeutic clinical study/received any investigational agent within 30 days of enrolment.

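### Protocol 6.2 permits anticoagulants on an INR condition that points the opposite way from 6.1, and lists drugs affecting neuromuscular transmission as both prohibited and usable with caution

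*Protocol*

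**What the plan says.** **INR.** The Note in Protocol 6.1 reads: "For subjects receiving antivitamin K therapy the Investigator will have to ensure that the International Normalised Ratio (INR) is below 3.5 within 1 week" before study treatment is given. Protocol 6.2 has a list that opens "The following concomitant medications are permitted during this study but they must be monitored closely", and its last bullet is "anticoagulant treatment if INR > 3.5 during the study". Neither section refers to the other on this point.

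**Drugs affecting neuromuscular transmission.** Another list in 6.2 opens "The following concomitant medications are not permitted during this study (see also Section 4.2"), and its second bullet reads "drugs which affect neuromuscular transmission, such as aminoglycoside antibiotics, should be used with caution". The other two bullets in that list, on other botulinum toxins and on anti-spasticity drugs expected to change dose, both state that the treatment is not allowed.

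**Related text.** Exclusion criterion 6 in Protocol 4.2 bars drugs that interfere with neuromuscular function if use is "Current, planned or received within the last 4 weeks prior to study treatment". Protocol 1.4 says of these drugs that "such drugs should be used with caution in patients treated with BTX", and of bleeding that "Dysport should be used only where strictly necessary in patients with prolonged bleeding times". Table 2, the visit lists in Protocol 5.2 and the SAP contain no INR item.

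**The concern.** Both rules bear on risks that the protocol itself names in section 1.4: intramuscular injection in patients who bleed longer, and a toxin effect that other drugs may enhance.

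On INR, a reader who takes the 6.2 bullet at its word finds anticoagulation expressly permitted on one side of 3.5, while 6.1 requires the other side before treatment. On the neuromuscular drugs, the heading prohibits and the bullet allows use with care; both cannot hold for the same drug.

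Two things are at stake. First, sites have no single readable rule for a subject on anticoagulants, or for one who comes to need, for example, an aminoglycoside after entry. Second, non-compliance can lead to withdrawal (Protocol 3.6 and 6.3), and major deviations decide who is in the per-protocol population (Protocol 10.1, SAP 2.2.3), which supports a planned secondary analysis (SAP 2.5). If the rule is unclear, so is what breaks it.

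**Working it through.** The check is one of text, so the provisions are set side by side. The only arithmetic concerns timing.

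**1. The two INR statements**

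| | Protocol 6.1 | Protocol 6.2 |
|---|---|---|
| Condition | INR < 3.5 | INR > 3.5 |
| Force | investigator must ensure | permitted, with close monitoring |
| Drugs | antivitamin K | anticoagulants in general |
| Time | within 1 week before study treatment | during the study |

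The values that 6.1 requires and those for which 6.2 gives express permission do not overlap, and an INR of exactly 3.5 is in neither set. The time windows do overlap: the second injection is given at Week 12, 16 or 20 of Cycle 1, so the week before it is also part of the study.

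The 6.2 bullet has two possible readings.
- *Condition of permission.* The bullet just before it, on anticholinergics, allows use if the dose has been stable, so there the word if introduces a condition. By analogy, 6.2 would permit anticoagulants only above 3.5 and leave 3.5 or below unaddressed.
- *Trigger for monitoring.* The lead-in asks for close monitoring, so the bullet could mean that anticoagulated subjects above 3.5 are to be watched. This is compatible with 6.1, but nothing in the text states it.

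**2. The neuromuscular drugs**

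Heading: not permitted. Bullet: use with caution. Criterion 6 already covers current, planned and recent use at entry, so the open case is an unplanned need after entry. Section 1.4 repeats the caution wording and does not settle the on-study status.

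**3. History**

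The Amendment 1 form records that a former exclusion for INR above 3.5 was deleted and that the 6.1 Note was added. The stated reason, in text that is partly broken, is that INR is a recommendation for dosing and not an exclusion. As far as the text can be read, the form's only entry for 6.2 changes BoNT-A to BoNT, and the Amendment 2 form has none. This fits a 6.2 bullet that was not revisited when the 6.1 Note came in. It is background only; the finding rests on the current text.

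**4. Who could still be on study**

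SAP 3.2.18 says that enrolment was already complete, without a date. SAP version 2.0 is dated 05 October 2018. Each cycle lasts at most 20 weeks plus a 7-day window: 20 × 7 + 7 = 147 days.
- Second injection still to come after that date: 05 October 2018 − 147 days = 11 May 2018, so only subjects first injected after 11 May 2018.
- Follow-up still to come: 2 × 147 = 294 days, and 05 October 2018 − 294 days = 15 December 2017, so only subjects first injected after 15 December 2017.

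Both dates assume the longest intervals and full use of the windows.

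**The case against.** The strongest reply is that no INR clash is proved. Section 6.1 is a duty tied to giving the injection; the 6.2 bullet is a permission for concomitant treatment and does not mention injection. A permission is not a requirement that INR exceed 3.5, so an antivitamin K subject below 3.5 breaches neither section. Anticoagulants are not on the prohibited list, and silence is not prohibition. The monitoring wording in the lead-in supports the harmless reading. This stands as far as it goes: the two sections are not strictly incompatible. It does not make the bullet clear, because the text does not choose between the readings, the parallel wording of the preceding bullet favours the literal one, and the two sections differ in drug scope.

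The inequality sign may also be a fault of the PDF reading. That cannot be excluded, and it is why the sign should be checked first.

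The amendment forms are visibly broken in places, so a count of logged changes may be incomplete. This is fair, and nothing depends on it. The lack of an INR item in Table 2 is not itself a defect either, since 6.1 gives the duty to the investigator; it shows only that the schedule does not settle the question.

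On timing, the first SAP version, which covered the baseline interim analysis, is dated 22 November 2017. If enrolment ended about then, the last visit would fall by about 12 September 2018 (22 November 2017 + 294 days), before SAP version 2.0, and a site notice would be moot. The date on which enrolment ended is not given, so this is possible but not shown. The deviation check would still apply.

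Finally, the neuromuscular point is narrow, since criterion 6 deals with entry. The contradiction between heading and bullet remains.

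**Conclusion.** The concern holds. Current protocol text leaves the INR condition for anticoagulated subjects open to two readings, one of which points the opposite way from 6.1, and gives drugs affecting neuromuscular transmission two incompatible on-study statuses. Neither the schedule, the exclusion criteria nor the SAP resolves them.

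The size cannot be given as a number of subjects: the documents do not report how many were anticoagulated or came to need a neuromuscular-transmission drug after entry. On the literal INR reading, the gap reaches every anticoagulated subject at 3.5 or below; on the monitoring reading, there is ambiguity but no clash. The primary mITT analysis is not affected. Any effect on the per-protocol set depends on the Protocol Deviation Document, which is not among the documents available. The INR half also assumes that the sign in 6.2 was read correctly. The point should be corrected because it concerns safety rules and the correction is cheap.

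**What to change.** 1. Check the inequality sign in the 6.2 anticoagulant bullet against the source page.
2. Reconcile 6.1 and 6.2 to one INR condition, stating which anticoagulants it covers and when it applies, with a cross-reference between the sections.
3. Give drugs affecting neuromuscular transmission a single on-study status in 6.2 that agrees with the heading they stand under and with Section 4.2.
4. Notify sites if any second injections or follow-up visits remain.
5. In any case, confirm that the Protocol Deviation Document matches the reconciled text before database lock; Protocol 10.1.2 already provides for a review of deviations at that point.

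The content of items 2 and 3 is for the sponsor's medical team; this review takes no position on which rule is right. The cost is a short protocol clarification, a site notice only if subjects are still on study, and one document check. No analysis changes.

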7 ASSESSMENT OF EFFICACY

For the timing of assessments in this study, refer to the schedule in Table 2.

7.1 Primary Efficacy Endpoint and Evaluation

The primary efficacy endpoint is as follows:

• the percentage of responder subjects at Week 6 after the second injection, according to composite AROM in the primary TT limb.

Composite AROM (X_A), regardless of whether the muscle groups were injected or not, as measured by goniometer in the primary TT limb (either UL or LL, depending on which one has been selected as the primary TT limb), will be calculated as follows:

- composite X_A UL: X_A UL = X_{AEF} + X_{AWF} + X_{AFF}
- composite $X_A LL$: $X_A LL = X_{Asol} + X_{AGN}$

where for UL: EF=elbow flexors, WF=wrist flexors and FF=extrinsic finger flexors, and for LL: Sol=soleus and GN=gastrocnemius muscles.

Definition of a responder: a subject will be considered a responder if he/she achieves at least the predefined improvement threshold - larger or equal to 35° in UL or 5° in LL - in the primary TT limb (based on the composite AROM individual change from baseline to Week 6 after the second injection).

